Ocular surface complications in primary open-angle glaucoma

Occurrence of the ocular surface complications in primary open-angle glaucoma patients
on treatment with IOP lowering eye drops

Project protocol, 04.09.2021.

Introduction:

Glaucoma is a chronic progressive optic neuropathy characterized by retinal ganglion cell death and optic nerve fiber layer loss that can cause progressive deterioration of the peripheral vision, and if left untreated, can lead to severe visual impairment and even blindness (Weinreb, Aung, & Medeiros, 2014). Elevated intraocular pressure (IOP) is the most consistent risk factor for developing glaucoma, and lowering it is the only recognized treatment method (Boland et al., 2013). Topical IOP-lowering eye drops are often used as the first line of treatment to reduce the intraocular pressure and prevent damage to the optic nerve; however, recent research indicates an association between topical treatment and ocular surface disease (OSD) (Zhang, Vadoothker, Munir, & Saeedi, 2019).

The prevalence of OSD in patients with glaucoma varies from 22% to 78%, depending on the specific test used (Baudouin et al., 2013; Fechtner et al., 2010; Leung, Medeiros, & Weinreb, 2008). Research agrees that glaucoma and ocular surface disease co-exist, and OSD often worsens with age, duration of the treatment, and a number of topical IOP lowering eye drops with and without preservatives (Baudouin et al., 2013; Stewart, Stewart, & Nelson, 2011). Dryness, fatigue, burning, variable visual acuity, and photophobia are the most common symptoms of OSD and can affect a patient's ability to work and quality of life (Leung et al., 2008; Zhang et al., 2019). Schwartz et al. demonstrated that 23 to 59% of patients are not adherent to prescribed therapy with topical IOP lowering medication, but it is unclear whether this is related to OSD (Schwartz & Quigley, 2008). A study by Boso et al. that investigated the impact of the OSD treatment in glaucoma patients (Boso, Gasperi, Fernandes, Costa, & Alves, 2020) showed that short-term treatment could improve signs and symptoms of OSD. A better understanding of the cause-effect relationship between OSD and glaucoma treatment with IOP-lowering eye drops may help individualize treatment options for patients in agreement with personalized medicine.

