Signs and symptoms of OSD are often non-specific to the ocular surface and caused by allergic, pro-inflammatory, or toxic conditions (Stewart et al., 2011). Ocular surface toxicity, especially to benzalkonium chloride (BAK) preservative, has been established and thoroughly discussed in the literature, which is why preservative-free treatment options are increasingly advocated, especially in patients already presenting with OSD (Stewart et al., 2011; Zhang et al., 2019). Performing a comprehensive tear film assessment in glaucoma patients may be beneficial and lead to a better understanding of the disease. To the best of our knowledge, no studies performed a full ocular surface assessment in glaucoma patients on topical treatment with IOP-lowering eye drops.

Research objectives and significance:

The main objective of the study is to investigate signs and symptoms of ocular surface disease in patients on topical glaucoma medications.

The main objective of the study is based on the following research questions:

1. What is the occurrence of signs and symptoms of ocular surface disease (OSD) in patients with primary open-angle glaucoma (POAG) who have been on treatment with IOP-lowering eye drops for at least three months?
2. Is the occurrence of signs and symptoms of OSD in patients with POAG related to added preservatives in the IOP-lowering eye drops?
3. Is the occurrence of signs and symptoms of OSD in patients with POAG modified by the active pharmacological substance in the IOP-lowering eye drops?

4. Is the occurrence of signs and symptoms of OSD in patients with POAG related to the duration of the treatment with the IOP-lowering eye drops?

Based on research questions 2-4, the following hypotheses were formulated:

1. In a sample of patients with POAG, who have been on treatment with IOP lowering eye drops for at least three months, the frequency of signs of OSD, defined as hyperosmolarity, reduced NIKBUT, ocular surface staining, or reduced Schirmer 1 test, is greater in patients that are on eye drops with preservatives compared with those that are not.
2. In a sample of patients with POAG, who have been on treatment with IOP lowering eye drops for at least three months, the frequency of symptoms of OSD, defined as OSDI index ≥ 13 or SPEED II values >5 , is greater in patients that are on eye drops with preservatives compared with those that are not.

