This study is a sub-study of an “Ocular Surface and glaucoma. A randomized study of IOP reducing eye drops versus surgical intervention” study (REK no. 253485). Invited to participate in the study are men and women between 50 and 75 years of age with early POAG, diagnosed in agreement with the European guidelines for glaucoma diagnoses and staging of the disease, with MD loss of less than 5 dB on visual fields and with a clinically significant cataract eligible for surgery, who come for a routine glaucoma follow-up examination and a presurgical assessment for cataract extraction at the ophthalmology practice of Ifocus Øyeklinikk in Haugesund, Norway, in the period between August 2021 and February 2022.

Exclusion criteria:

- Recent changes (<3 months) in the treatment with topical IOP-lowering medications (i.e., active pharmacological substance, dosage, preservatives) based on the patient medical journals.
- Use of more than one IOP-lowering eyedrops with different active pharmacological substances based on the patient medical journals.
- Self-reported OSD comorbidity defined as an autoimmune or inflammatory disease, such as Sjogren’s syndrome or Rheumatoid Arthritis (RA), or any other systemic disease that can directly affect the ocular surface.
- Conditions that may confound the results of the study:
 - Self-reported acute or chronic diseases such as connective tissue disease, clinically significant atopic disease, diabetes type 1 and 2, immunocompromised, or any other such condition.
 - Manifest corneal disease, dystrophy, or scarring based on the clinical exam.
 - Corneal ectasia based on the clinical exam.
 - Lid deformities based on the clinical exam.

- Recent intra- or extra-ocular surgery based on the patient medical journals.
- Previous refractive procedures like LASIK, LASEK, or radial keratotomy based on the patient medical journals.
- A previous corneal transplant, DSAEK, lamellar keratoplasty, or similar procedure based on the patient medical journals.

Recruitment:

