Corneal sensitivity is defined as the ability of the cornea to sense a variety of stimuli. Operationally, it is defined as the threshold for corneal surface to sense the touch of a fine nylon filament (0,12 mm) applied to the corneal apex by means of a Cochet-Bonnet Aesthesiometer (Luneau Technology Group). The length of the nylon filament can be adjusted (from 60 mm (highest sensitivity) to 5 mm (lowest sensitivity)). It is measured in millimeters and registered with one decimal on a numerical scale for the right and the left eye.

Meibomian gland dropout is defined as partial or total loss of acinar tissue of the meibomian glands and its function in the upper and lower eyelid. Operationally, meibomian gland dropout is defined as changes in the morphological appearance in the meibomian glands of the upper and the lower eyelid evaluated by means of infrared trans-illumination of the lids using an Oculus Keratograph 5M (OCULUS, Inc). Gland tissues are made visible using Meibo-Scan software and classified on the Meiboscale grading scale from a photograph taken with Oculus Keratograph 5M (Pult & Riede-Pult, 2013). It is registered in whole numbers on an ordinal scale that ranges from 0 to 4 (0=0% loss; 1= \leq 25%; 2=26%-50%; 3=51%-75%; 4= \rightarrow 75%) for the right and the left eye.

Predictor variables:

Preservative is defined as a substance or a chemical that is added to pharmaceutical drugs and other products to prevent decomposition by microbial growth or by undesirable chemical changes. Operationally, a preservative is defined as any of the following substances in the specification of the prescribed eye drops during the period of three months before inclusion into the study: Benzalkonium chloride, Polyquaternium-1, and Boric acid. The preservative is registered on a dichotomous scale where preservative=1 and no preservative=0.

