Active pharmacological substance is an ingredient used in a finished pharmaceutical product, intended to provide pharmacological activity or to otherwise have a direct effect in the diagnosis, cure, treatment, or prevention of disease. Operationally, the active pharmacological substance is defined as any of the following substances in the specification of the prescribed eye drops during the period of 3 months before inclusion into the study: prostaglandin analogs, beta-blocker, carbohydrase inhibitor, or alfa-2-agonist. The active pharmacological substance used by the patients will be known from the patient history and will be noted on a nominal scale (1= prostaglandin analogs, 2=beta-blocker, 3=carbohydrase inhibitor, 4= alfa-2-agonist).

The duration of the treatment is defined as the period in which the patient has been treated with the same pharmacological substance. Operationally, it is defined as information about the duration of the treatment collected from the medical records and registered on a numerical scale with the whole number of months of use.

Self-reported compliance is defined as an act complying or adhering to requirements (prescribed treatment). Operationally, it is defined as self-reported adherence to taking drops in agreement with the prescription measured by means of a simple interview question of how often one may skip a dose (0: Less than once or twice a month; 1: Once or twice a month; 2: Approximately once a week; 3: More than once a week). It will be registered on an ordinal scale.

Other variables:

Age will be registered as the whole number of years on a numerical scale.

Sex will be registered as female=1 and male=0 on a dichotomous scale.

Methods:

Recruitment:

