measurement is automatically stopped by the device if the patient moves or blinks. **Bulbar redness** will be measured and graded automatically and objectively by taking a picture with the Oculus Keratograph 5M. Similarly, **Tear Meniscus Height (TMH)** will be measured objectively from the picture taken with Oculus Keratograph 5M that has an integrated ruler and various magnification options. Following, **Schirmer 1 test** will be performed without anesthetics. The free end of the non-toxic calibrated filter paper will be placed in the temporal part of the lower eyelid of both eyes, and the patient will be asked to hold the eyes gently closed for 5 minutes. At the end of the 5-minute interval, the paper strips will be removed from each lower eyelid, and the amount of wetting of the paper will be noted. Slit-lamp examination of the anterior segment will be performed in order to evaluate **Ocular surface staining (OSS)**. A quantified 5 µl of 2% Fluorescein sodium will be instilled into each conjunctival sac with a micro-pipette (using a sterile tip), and then observation will be done with a slit-lamp using a yellow filter and cobalt blue light. **Meibum quality** and **Meibum expressibility** will be also evaluated during the slit lamp exam. Meibum quality will be assessed in each of the eight glands of the central third of the lower lid by applying pressure on the eyelid with a Q-tip. It will be estimated and graded on a scale from 0 to 3 for each gland: 0=clear, 1= cloudy, 2= cloudy with debris (granular), and 3= thick, like toothpaste (total score range, 0–24) (Nichols et al., 2011). **Meibum expressibility** will be assessed in the five central glands in the lower lid by applying pressure on the lid with a Q-tip. It will be estimated on a scale from 0-3 (0= all glands expressible; 1=3-4 glands expressible; 2= 1-2 glands expressible; 3=no glands expressible) according to the number of glands expressible (Nichols et al., 2011). **Cochet – Bonnet Aesthesiometer** will be used to measure corneal sensitivity. Fine nylon filament, the length of which can be adjusted (60 mm to 5 mm), will be used to apply different intensities of stimuli on the corneal surface. The shortest length of the filament that the patient reacts will be noted. **Meibomian gland dropout (Meibography)** will be measured by taking infrared photos of the upper and lower eyelid with Oculus Keratograph 5M with minimal discomfort to the patient. Gland tissues will be made visible by everting the upper and lower eyelids with a Q-tip and using Meibo-Scan. The degree of Meibomian dropout will be scored and noted for all four eyelids. Finally, **Self-reported compliance** will be examined by means of simple interview question of how often one may skip a dose (Appendix 4). Information's about age, gender, duration of the treatment, the active pharmacological substance, and the preservatives in the topical IOP-lowering medication will be collected from the patient journals.

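### Exposure in hypotheses 1-6 is taken from prescriptions and journals, so a patient who has stopped the drops without a journal entry is counted as on treatment, and the compliance question cannot identify that patient

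*Protocol*

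**What the plan says.** Research question 1 defines the patients of interest as those "who have been on treatment with IOP-lowering eye drops for at least three months", and hypotheses 1-6 repeat that condition. The protocol then fixes each part of exposure as follows.

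- **Preservative** (Predictor variables) is any listed substance "in the specification of the prescribed eye drops during the period of three months before inclusion into the study". The active substance is likewise defined by the prescribed drops over the same window.
- **Duration** (Predictor variables) is "collected from the medical records and registered on a numerical scale with the whole number of months of use".
- **Source at data collection** (Methods, Measurements): together with duration, "the active pharmacological substance, and the preservatives in the topical IOP-lowering medication will be collected from the patient journals".
- **Three-month stability** (Exclusion criteria) is judged from the same source: "Recent changes (<3 months) in the treatment with topical IOP-lowering medications (i.e., active pharmacological substance, dosage, preservatives) based on the patient medical journals".
- **Actual use** is covered by one interview question on skipped doses, asked last at the visit. Its four answers end with "3: More than once a week". That answer matches the definition of poor compliance in the secondary hypotheses. Compliance appears only in those hypotheses.

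The Introduction cites a report that "23 to 59% of patients are not adherent to prescribed therapy with topical IOP lowering medication", and adds that a link with ocular surface disease is unclear.

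**The concern.** The hypotheses are worded in terms of being on treatment and the duration variable in months of use, but what is recorded is what was prescribed. A patient who stopped two months ago, with nothing in the journal, meets every criterion. That patient is coded with the prescribed substance and preservative and credited with the full number of months.

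Two comparisons are affected. In hypotheses 1-6, such patients sit in exposed groups without the exposure, which tends to weaken the preservative, substance and duration associations. In the secondary hypotheses, the poor-compliance group mixes patients who miss two doses a week with patients who use nothing. The first may skip because the drops irritate; the second no longer have the exposure. Secondary hypotheses 3 and 4 also adjust for preservative, substance and duration, and those covariates are wrong for anyone who has stopped.

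The study has a single visit, so if the answer options do not separate these patients, no later analysis can.

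**Working it through.** **1. Can the plan detect an unrecorded stop?** Take a patient who stopped without a journal entry and follow the protocol's steps.

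| Step | Source | Result for this patient |
|---|---|---|
| Recent-change exclusion | Journals | Not triggered |
| Preservative and substance | Prescribed drops, journals | Coded as prescribed |
| Duration | Medical records | Full months |
| Compliance question | Interview, end of visit | Presumably code 3, as for a patient skipping two doses a week |
| Use of that answer in hypotheses 1-6 | No rule | None |

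A stop that is recorded in the journal could be caught, either as a recent change or because the patient is plainly not on topical treatment. The gap concerns unrecorded stops only.

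**2. Size in hypotheses 1-6.** The protocol gives no effect size or power figure to reproduce; its 30 subjects are a feasibility number. All rates below are assumptions: signs in 60% of preserved-drop users and 30% otherwise, stopped patients at the 30% rate, and an equal split of 15 and 15. With a share s of the preserved group stopped:

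observed difference = [0.60(1 - s) + 0.30s] - 0.30 = 0.30(1 - s)

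- One of 15 stopped: 0.30 × 14/15 = 0.28
- Two of 15 stopped: 0.30 × 13/15 = 0.26
- s = 10%, 20%, 30%: 0.27, 0.24, 0.21. The last two need 3 and 4.5 of 15 patients to have stopped.

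Standard error of the undiluted difference: sqrt(0.60 × 0.40/15 + 0.30 × 0.70/15) = sqrt(0.016 + 0.014) = 0.173, about 17 points.

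**3. Effect on power.** This uses a larger assumed contrast (70% against 30%, 15 per group, two-sided 5% level; the protocol does not state sidedness). The diluted rate is 0.70(1 - s) + 0.30s.

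| s | Difference (points) | Odds ratio | Power | n per group for 80% power |
|---|---|---|---|---|
| 0 | 40 | 5.4 | 60% | 24 |
| 5% | 38 | 5.0 | 55% | 26 |
| 10% | 36 | 4.5 | 51% | 30 |
| 23% | 31 | 3.6 | 39% | 40 |

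The 23% row would require every non-adherent patient, at the low end of the cited range, to have stopped completely. It is a bounding case, not an estimate.

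**4. Size in the compliance comparison.** Assume 30% positive among stopped patients, 90% among those who skip because of ocular surface disease, and 60% among regular users. The poor-compliance group then averages:

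- half stopped: 0.50 × 0.30 + 0.50 × 0.90 = 0.60, equal to regular users
- a quarter stopped: 0.25 × 0.30 + 0.75 × 0.90 = 0.75
- three quarters stopped: 0.75 × 0.30 + 0.25 × 0.90 = 0.45

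The result can lie above, at or below 60%, depending on a mix that the data as planned cannot reveal. Exact cancellation needs one particular mix.

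**The case against.** The protocol says openly that preservative and substance are defined by prescription. Prescribed exposure is a coherent definition for a cross-sectional study that measures adherence separately. A stopped patient would correctly fall under poor compliance, and secondary hypotheses 3 and 4 look at compliance together with the three exposures. Participants attend routine glaucoma follow-up. Of the substance the protocol also says "The active pharmacological substance used by the patients will be known from the patient history", which could mean an interview. The form carrying the compliance question is an appendix that is not available here. A with-and-without analysis could be left to a statistical analysis plan.

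Part of this stands. The definition is disclosed, and the sample of 30 limits precision far more than a stopped patient or two would. But the hypotheses and the duration variable are worded as treatment and use, not prescription. The Measurements section names the journals as the source. The body text fixes four answers, none of which identifies a patient who has stopped. An analysis plan cannot recover information that was never collected.

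Two stronger readings are tempting. A reader might take the cited 23 to 59% as the share that has stopped; it is non-adherence in general, and the protocol gives no figure for stopping. A reader might also infer that the compliance comparison will falsely show no relationship; the mix that cancels exactly was chosen to do so and shows only that cancellation is possible.

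**Conclusion.** The point holds as a gap in how exposure is ascertained. The protocol's three-month on-treatment condition is not verified for hypotheses 1-6, and an unrecorded stop is coded as full exposure and then merged with occasional skipping in the secondary hypotheses.

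The number of affected patients is unknown and probably small. With one or two among an assumed 15, dilution is 2 to 4 points of an assumed 30, well within the sampling error of about 17 points. This rests on an equal split and on stopped patients having the same rate as users of preservative-free drops, neither of which the protocol supports or contradicts. If ocular surface disease itself prompts stopping, misclassification depends on the outcome and need not act as simple dilution. The point is worth correcting because it is cheap and cannot be repaired after the visit, not because it threatens the study.

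**What to change.** 1. In Self-reported compliance (Predictor variables), and on the form used at the visit, add an answer that separates patients still using the drops from patients not currently using them, and record since when.
2. Ask it at the study visit after consent is signed. The appointment telephone call is not suitable: consent is signed at the appointment, and the ethics section requires it before any data are collected.
3. Use the answer to confirm the protocol's own three-month on-treatment condition. The documents give no basis for any other cut-off for non-use.
4. Show hypotheses 1-6 with and without patients who do not meet that condition. In the secondary hypotheses, describe them separately from patients who skip doses. With perhaps one or two patients this will be descriptive, and the Analyses section's provision for combining sparse categories should not merge them back without saying so.

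The cost is one more answer option and one extra line of results. The drawbacks are possibly one or two fewer patients in one version of hypotheses 1-6, and an answer that is still self-reported. The fix concerns measurement and analysis only and directs no treatment.

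### The corneal-sensitivity recording rule asks for the shortest filament length felt, but on the protocol's own scale the threshold is the longest length felt

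*Protocol*

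**What the plan says.** Two places in the Protocol govern this variable.

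- **Outcome variables, corneal sensitivity.** The operational definition is "the threshold for corneal surface to sense the touch of a fine nylon filament". The adjustable length runs "from 60 mm (highest sensitivity) to 5 mm (lowest sensitivity". On the type of variable: "It is measured in millimeters and registered with one decimal on a numerical scale for the right and the left eye".
- **Methods, Measurements, Cochet-Bonnet aesthesiometer.** Changing the filament length "will be used to apply different intensities of stimuli on the corneal surface". The recording rule is: "The shortest length of the filament that the patient reacts will be noted".

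The Measurements section gives the range of lengths but no starting length, step size, order of presentation or stopping rule.

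**The concern.** The definition and the recording rule point in opposite directions. A threshold is the weakest stimulus that is still sensed. If sensing the 60 mm filament marks the highest sensitivity, the long filament must be the weak stimulus and the short one the strong stimulus. The threshold is then the greatest length that gets a response, whereas the rule tells the examiner to note the smallest.

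What is at stake is whether the recorded number measures corneal sensitivity at all. The Analyses section plans means, standard deviations and ANOVA for continuous variables, and a value that is the same for nearly everyone would tell nothing there. The data check described in that section flags empty cells and unrealistic values. A reading of 5 mm lies on the stated scale, so that check as described gives no reason to flag it. The sub-study has a single appointment and so plans no later visit at which a misrecorded value could be measured again.

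**Working it through.** The protocol gives no figure to reproduce here, so the check is a logical one.

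**Inputs from the Protocol**
- The outcome is the touch threshold (Outcome variables, corneal sensitivity).
- 60 mm is the highest sensitivity and 5 mm the lowest (same place).
- The recorded value is the shortest length that gets a reaction (Measurements).

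**Assumptions, not in the Protocol**
- Lengths change in 5 mm steps, which gives 12 levels: 60, 55, ..., 5 mm.
- The response is monotone: a patient who reacts to one length reacts to every shorter, stiffer one.
- Failures to respond to a felt stimulus (lapses) occur at a rate between 0 and 10%.

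**Step 1: set of lengths felt.** On the stated scale, a patient with threshold *t* feels every length L with 5 ≤ L ≤ *t*. The largest member of this set is *t*. The smallest is 5 mm, whatever *t* is.

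**Step 2: full range presented, no lapses.**

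| True threshold (mm) | Longest length felt | Shortest length felt |
|---|---|---|
| 60 | 60 | 5 |
| 45 | 45 | 5 |
| 20 | 20 | 5 |
| 5 | 5 | 5 |

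Over all 12 levels, the longest length equals the threshold 12 times out of 12. The shortest is 5 mm 12 times out of 12.

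**Step 3: allow lapses.** A patient with any sensation is recorded as 5 mm unless the response at 5 mm itself is missed, so the proportion recorded as 5 mm is 1 − lapse rate. A simulation with thresholds drawn evenly over the 12 levels agrees:

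| Lapse rate | 1 − lapse rate | Simulated |
|---|---|---|
| 0% | 100% | 100% |
| 2% | 98% | 98.1% |
| 5% | 95% | 95.0% |
| 10% | 90% | 89.9% |

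**Step 4: does any scale rescue the wording?** If the scale is reversed, so that a patient feels every length at or above *t*, the shortest length felt equals *t* at all 12 levels. The rule as worded is therefore right only on a scale that the outcome definition excludes.

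**Step 5: does any procedure rescue the wording?** If the filament starts at 60 mm, is shortened, and testing stops at the first reaction, then only one presented length has been felt. It is both the shortest and the longest such length, and it equals *t*. The rule then does no harm, but this sequence is not written down.

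**Step 6: effect on the planned analysis in the literal case.** If all values are 5 mm, every group mean is 5, so the between-group and within-group sums of squares are both 0. The ANOVA F ratio is then 0/0, and no comparison is possible.

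**The case against.** The best defence is practical. All examinations are done by one experienced observer, and both sections write the range downwards, from 60 to 5 mm. Such an observer may well shorten from 60 mm and stop at the first reaction, which records the threshold. A column of 5 mm values would also mean the lowest possible sensitivity in everyone, and the observer would probably notice.

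Most of this stands as a limit on the consequence. A reader might infer that nearly every participant will be recorded as 5 mm. The Protocol does not support that as a prediction: it requires testing to go on to 5 mm after a reaction has already occurred, and the Protocol does not say so. The 12-of-12 result and the lapse figures rest on the assumptions listed above. A reader might also infer that the data will mix two opposite readings from different examiners. With a single observer named for all examinations, that is unlikely.

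The defence does not remove the contradiction. The range is given as what the instrument can be set to, not as a sequence of presentation. The benign reading therefore relies on a procedure that is absent from the Protocol, while the rule that is present points the wrong way. Nor is this a detail that could be left to an analysis plan, because it is a data-collection rule that the Protocol itself states.

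**Conclusion.** The contradiction is established from the Protocol alone: the definition and scale make the threshold the longest length felt, and the recording rule names the shortest. Nothing elsewhere in the document corrects it.

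Its size depends on how the test is run. Under literal use over the full range with a monotone response, the 5 to 60 mm scale collapses to 5 mm for every patient with any sensation. Under shortening from 60 mm with a stop at the first reaction, nothing is lost. The Protocol does not say which applies.

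I rate this minor to moderate. Corneal sensitivity is a listed outcome that serves the descriptive objective and the general group comparisons. It might be inferred that the error undermines the hypothesis tests, but it does not. The six main and four secondary hypotheses define signs of OSD by osmolarity, NIKBUT, staining and Schirmer 1, and symptoms by OSDI and SPEED II. Losing this variable entirely would leave all ten untouched.

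**What to change.** In the Measurements section, replace shortest with longest, so that the recorded value for each eye is the threshold on the scale already defined under Outcome variables (larger mm = higher sensitivity). It is preferable also to state that the filament is shortened from 60 mm until the first reaction. The sequence is a clarification; the one-word change is what removes the contradiction.

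Recruitment is planned from August 2021 and the Protocol is dated 04.09.2021, so the sponsor should confirm which length was noted for any patient already examined.

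The cost is one sentence of text and a check of any existing records. No procedure, visit or equipment is added.
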